5.3.1.3 Dose Interruptions and Modifications for Pembrolizumab

Adverse events (both non-serious and serious) associated with pembrolizumab exposure may represent an immunologic etiology. These adverse events may occur shortly after the first dose or several months after the last dose of treatment. Pembrolizumab must be withheld for drug-related toxicities and severe or life-threatening AEs as per 3 below. See Section 5.5.1 for supportive care guidelines, including use of corticosteroids.

Table 7: Dose Modification Guidelines for Pembrolizumab Adverse Events (AEs)

Toxicity	Hold Treatment For Grade	Timing for Restarting Treatment	Treatment Discontinuation
Diarrhea/Colitis	2-3	Toxicity resolves to Grade 0-1	Toxicity does not resolve within 12 weeks of last dose or inability to reduce corticosteroid to 10 mg or less of prednisone or equivalent per day within 12 weeks
	4	Permanently discontinue	Permanently discontinue
AST, ALT, or Increased Bilirubin	2	Toxicity resolves to Grade 0-1	Toxicity does not resolve within 12 weeks of last dose
	3-4	Permanently discontinue (see exception below) ^a	Permanently discontinue
Type 1 diabetes mellitus (if new onset) or Hyperglycemia	T1DM or 3-4	Hold pembrolizumab for new onset Type 1 diabetes mellitus or Grade 3-4 hyperglycemia associated with evidence of beta cell failure	Resume pembrolizumab when patients are clinically and metabolically stable
Hypophysitis	2-4	Toxicity resolves to Grade 0-1. Therapy with pembrolizumab can be continued while endocrine replacement therapy is instituted	Toxicity does not resolve within 12 weeks of last dose or inability to reduce corticosteroid to 10 mg or less of prednisone or equivalent per day within 12 weeks
Hyperthyroidism	3	Toxicity resolves to Grade 0-1	Toxicity does not resolve within 12 weeks of last dose or inability to reduce corticosteroid to 10 mg or less of prednisone or equivalent per day within 12 weeks
	4	Permanently discontinue	Permanently discontinue
Hypothyroidism		Therapy with pembrolizumab can be continued while thyroid replacement therapy is instituted	Therapy with pembrolizumab can be continued while thyroid replacement therapy is instituted
Infusion Reaction	2 ^b	Toxicity resolves to Grade 0-1	Permanently discontinue if toxicity develops despite adequate premedication
	3-4	Permanently discontinue	Permanently discontinue

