Pneumonitis	2	Toxicity resolves to Grade 0-1	Toxicity does not resolve within 12 weeks of last dose or inability to reduce corticosteroid to 10 mg or less of prednisone or equivalent per day within 12 weeks Or 2 nd episode
	3-4	Permanently discontinue	Permanently discontinue
Renal Failure or Nephritis	2	Toxicity resolves to Grade 0-1	Toxicity does not resolve within 12 weeks of last dose or inability to reduce corticosteroid to 10 mg or less of prednisone or equivalent per day within 12 weeks
	3-4	Permanently discontinue	Permanently discontinue

Toxicity	Hold Treatment For Grade	Timing for Restarting Treatment	Treatment Discontinuation
All Other Drug-Related Toxicity ^c	3 or Severe	Toxicity resolves to Grade 0-1	Toxicity does not resolve within 12 weeks of last dose or inability to reduce corticosteroid to 10 mg or less of prednisone or equivalent per day within 12 weeks
	4	Permanently discontinue	Permanently discontinue

Note: Permanently discontinue for any severe or Grade 3 drug-related AE that recurs or any life-threatening event.

^a For patients with liver metastasis who begin treatment with Grade 2 AST or ALT, if AST or ALT increases by greater than or equal to 50% relative to baseline and lasts for at least 1 week then patients should be discontinued.

^b If symptoms resolve within one hour of stopping drug infusion, the infusion may be restarted at 50% of the original infusion rate (e.g., from 100 mL/hr to 50 mL/hr). Otherwise dosing will be held until symptoms resolve and the subject should be premedicated for the next scheduled dose.

^c Patients with intolerable or persistent Grade 2 drug-related AE may hold study medication at physician discretion. Permanently discontinue study drug for persistent Grade 2 adverse reactions for which treatment with study drug has been held, that do not recover to Grade 0-1 within 12 weeks of the last dose.

Dosing interruptions are permitted in the case of medical / surgical events or logistical reasons not related to study therapy (e.g., elective surgery, unrelated medical events, subject vacation, and/or holidays). Subjects should be placed back on study therapy within 3 weeks of the scheduled interruption, unless otherwise discussed with the Sponsor (NYU Langone Medical Center). The reason for interruption should be documented in the subject's study record.

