Hyperthyroidism	Grade 2	Continue	
 Treat with non-selective beta-blockers (e.g. propranolol) or thionamides as appropriate 	
 Monitor for signs and symptoms of thyroid disorders.
	Grade 3 or 4	Withhold or Permanently discontinue		

General instructions:				
Immune-related AEs	Toxicity grade or conditions (CTCAEv4.0)	Action taken to pembrolizumab	irAE management with corticosteroid and/or other therapies	Monitor and follow-up
Hypothyroidism	Grade 2-4	Continue	
 Initiate thyroid replacement hormones (e.g. levothyroxine or liothyroinone) per standard of care 	
 Monitor for signs and symptoms of thyroid disorders.
Nephritis and renal dysfunction	Grade 2	Withhold	
 Administer corticosteroids (prednisone 1-2 mg/kg or equivalent) followed by taper. 	
 Monitor changes of renal function
	Grade 3 or 4	Permanently discontinue		
All Other immune-related AEs	Grade 3, or intolerable/ persistent Grade 2	Withhold	
 Based on severity of AE administer corticosteroids 	
 Ensure adequate evaluation to confirm etiology or exclude other causes
	Grade 4 or recurrent Grade 3	Permanently discontinue		

NOTES:

- Withhold or permanently discontinue pembrolizumab is at the discretion of the investigator or treating physician.
- For subjects with Grade 3 or 4 immune-related endocrinopathy where withhold of pembrolizumab is required, pembrolizumab may be resumed when AE resolves to \leq Grade 2 and is controlled with hormonal replacement therapy or achieved metabolic control (in case of T1DM).

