5.7 Subject Withdrawal/Discontinuation Criteria

Subjects may withdraw consent at any time for any reason or be dropped from the trial at the discretion of the investigator should any untoward effect occur. In addition, a subject may be withdrawn by the investigator or the Sponsor if enrollment into the trial is inappropriate, the trial plan is violated, or for administrative and/or other safety reasons. Specific details regarding discontinuation or withdrawal are provided in Section 7.1.4 – Other Procedures.

A subject must be discontinued from the trial treatment for any of the following reasons:

- The subject or legal representative (such as a parent or legal guardian) withdraws consent.
- Confirmed radiographic disease progression

Note: For unconfirmed radiographic disease progression, please see Section 7.1.2.5

Note: A subject may be granted an exception to continue on treatment with confirmed radiographic progression if clinically stable or clinically improved, please see Section 7.1.5.3.5.

- Unacceptable adverse experiences as described in Section 5.3
- Intercurrent illness that prevents further administration of treatment
- Investigator's decision to withdraw the subject
- The subject has a confirmed positive serum pregnancy test
- Noncompliance with trial treatment or procedure requirements
- The subject is lost to follow-up
- Administrative reasons

The End of Treatment and Follow-up visit procedures are listed in Section 6.0 (Study Flow Chart) and Section 7.1.5 (Visit Requirements). After the end of treatment, each subject will be followed for 30 days for adverse event monitoring (serious adverse events will be collected for 90 days after the end of treatment as described in Section 7.2). Subjects who discontinue for reasons other than progressive disease will have post-treatment follow-up for disease status until disease progression, initiating a non-study cancer treatment, withdrawing consent or becoming lost to follow-up. After documented disease progression each subject will be followed by telephone for overall survival until death, withdrawal of consent, or the end of the study, whichever occurs first.

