7.2.5 Evaluating Adverse Events

An investigator who is a qualified physician will evaluate all adverse events according to the NCI Common Terminology for Adverse Events (CTCAE), version 4.03. Any adverse event which changes CTCAE grade over the course of a given episode will have each change of grade recorded on the adverse event case report forms/worksheets.

All adverse events regardless of CTCAE grade must also be evaluated for seriousness.

Table 13: Evaluating Adverse Events

An investigator who is a qualified physician, will evaluate all adverse events as to:

V4.0 CTCAE Grading	Grade 1	Mild; asymptomatic or mild symptoms; clinical or diagnostic observations only; intervention not indicated.
	Grade 2	Moderate; minimal, local or noninvasive intervention indicated; limiting age-appropriate instrumental ADL.
	Grade 3	Severe or medically significant but not immediately life-threatening; hospitalization or prolongation of hospitalization indicated; disabling; limiting self-care ADL.
	Grade 4	Life threatening consequences; urgent intervention indicated.
	Grade 5	Death related to AE
Seriousness	A serious adverse event is any adverse event occurring at any dose or during any use of Merck product that:	
	† Results in death; or	
	† Is life threatening; or places the subject, in the view of the investigator, at immediate risk of death from the event as it occurred (Note: This does not include an adverse event that, had it occurred in a more severe form, might have caused death.); or	
	† Results in a persistent or significant disability/incapacity (substantial disruption of one's ability to conduct normal life functions); or	
	† Results in or prolongs an existing inpatient hospitalization (hospitalization is defined as an inpatient admission, regardless of length of stay, even if the hospitalization is a precautionary measure for continued observation. (Note: Hospitalization for an elective procedure to treat a pre-existing condition that has not worsened is not a serious adverse event. A pre-existing condition is a clinical condition that is diagnosed prior to the use of a Merck product and is documented in the patient's medical history.); or	
	† Is a congenital anomaly/birth defect (in offspring of subject taking the product regardless of time to diagnosis); or	

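### Pembrolizumab hold, stop and restart rules conflict in a limited set of places, mainly for severe endocrine toxicity, and no table is named as governing

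*Combined protocol and SAP*

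**What the plan says.** Section 5.3.1.3 is written as an obligation: "Pembrolizumab must be withheld for drug-related toxicities and severe or life-threatening AEs as per 3 below". The cross-reference appears to have lost its table name; Table 7 follows directly. It sets out, by toxicity and grade, when to hold, restart and stop for good. A note beneath it says: "Permanently discontinue for any severe or Grade 3 drug-related AE that recurs or any life-threatening event". Section 5.7 adds "A subject must be discontinued from the trial treatment for any of the following reasons", and its list includes "Unacceptable adverse experiences as described in Section 5.3".

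Table 9 in Section 5.5.1 also has dose modification in its title and a column for the action on pembrolizumab. Two notes follow it. The first says: "Withhold or permanently discontinue pembrolizumab is at the discretion of the investigator or treating physician". It names no row and no grade. The second allows restart after a Grade 3 or 4 immune-related endocrine event that required a hold, once the event is at Grade 2 or lower and controlled.

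Two Table 7 rows that reach Grade 4 do not end in a permanent stop. For new type 1 diabetes or Grade 3-4 hyperglycemia, the last column reads: "Resume pembrolizumab when patients are clinically and metabolically stable". The hypophysitis row (Grades 2-4) gives restart at Grade 0-1 and also allows dosing to go on during hormone replacement. Table 13 in Section 7.2.5 describes Grade 4 as "Life threatening consequences; urgent intervention indicated".

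**The concern.** Hold and stop rules limit re-exposure after a severe immune event. They carry extra weight here because the trial is multi-site (Sections 5.2.2 and 5.2.3) and Section 7.2.7 sets no formal stopping rules. Where two current passages give different actions for the same event, sites can diverge while each follows the protocol, and a monitor cannot say which action was a deviation.

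There is a smaller analysis consequence. Under Section 8.1, one route to being response evaluable is receiving both agents for at least 2 cycles. A difference in stopping could affect that, but only for an event within those first cycles. The documents give no timing data from which to estimate it, and the Simon design figures do not depend on it.

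**Working it through.** The plan states no figure on this point, so the check is a comparison of text, followed by a rough sizing.

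**Step 1: mandatory or discretionary.** Sections 5.3.1.3 and 5.7 oblige; the first Table 9 note permits. Its scope is unstated. Its action wording matches that of two Table 9 cells, hypophysitis and hyperthyroidism at Grade 3 or 4, so it may be meant only for those. No sentence says so.

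**Step 2: Table 7 against Table 9.**

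| Event | Table 7 (Section 5.3.1.3) | Table 9 (Section 5.5.1) |
|---|---|---|
| Hyperthyroidism, Grade 4 | Permanent discontinuation | Either hold or permanent discontinuation |
| Hypophysitis, Grade 3-4 | Hold with restart, or continue with replacement | Either hold or permanent discontinuation |
| Restart threshold after a Grade 3-4 endocrine event | Grade 0-1 (hypophysitis; Grade 3 hyperthyroidism) | Grade 2 or lower, with control |

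**Step 3: Table 7 against its own note.** Nine Table 7 rows explicitly cover Grade 4.

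- Seven agree with the note: diarrhea/colitis, liver tests (with a declared liver-metastasis exception), hyperthyroidism, infusion reaction, pneumonitis, renal, and all other.
- Two do not: hypophysitis and type 1 diabetes/hyperglycemia.
- Hypothyroidism has no grade and says continue, so it would conflict only for a Grade 4 event.

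The liver row flags its exception; the two endocrine rows flag none. For diabetes/hyperglycemia both tables hold and then allow resumption, so that conflict is with the Table 7 note alone. Grade 4 hypophysitis is the clearest case: stop under the note, hold or continue under its Table 7 row, hold or stop under Table 9.

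**Step 4: size.** The documents give no endocrine event rates for this combination. Section 4.1.2.6 gives pembrolizumab monotherapy rates:

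- Hyperthyroidism as an event of significant interest: 2.2%. 29 × 0.022 = 0.64.
- Remaining events of significant interest: 0.1% to 1.3%. Assuming hypophysitis and type 1 diabetes each sit at the 1.3% top: 29 × 0.013 = 0.38 each.
- Serious drug-related hyperthyroidism and hypophysitis: 0.3% each. 29 × 0.003 = 0.09 each.

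High end: 29 × (0.022 + 0.013 + 0.013) = 1.4 subjects. This is not restricted to Grade 3-4, so it overstates on that count. Low end: 29 × (0.003 + 0.003) = 0.17, about 0.2 subjects. This leaves out diabetes. Neither figure allows for any contribution from lenvatinib.

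**The case against.** The documents lean towards Section 5.3. Section 5.5.1 calls its measures suggested and points to Section 5.3.1.3 for dose modification; Section 5.7 ties mandatory stopping to Section 5.3. The Table 9 note can be read as saying only who chooses between holding and stopping in the two cells with matching wording, and on that reading it does not license continued dosing. Table 7 already gives discretion for some Grade 2 events (footnote c). A specific row may be taken to qualify a general note. Grade 4 also need not always mean life-threatening: Table 8 footnote d, for lenvatinib, recognizes laboratory abnormalities that are not.

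Much of this stands as a limit on the point, but it does not remove it. The pointer in Section 5.5.1 sits in the note on events judged unrelated, so it sets no clear precedence, and Table 9 claims dose modification in its own title. Even on the narrow reading of the note, the tables still differ on Grade 4 hyperthyroidism and on the restart threshold. The Table 8 footnote weakens the hyperglycemia conflict, which needs an event that is truly life-threatening, but leaves the Table 7 note without a stated endocrine exception.

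A reader might go further in four ways that the documents do not support:

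- **That the Table 9 note overrides every mandatory row, Grade 3-4 pneumonitis included.** This needs the broadest reading of a note whose wording echoes two endocrine cells.
- **That Table 7's note contradicts its Grade 4 rows generally.** Seven of nine agree.
- **That the tables contradict each other on recurrent Grade 3 diarrhea/colitis.** The rows match; the Table 7 note addresses recurrence and Table 9's row is silent.
- **That 5 to 9 of 29 subjects are affected**, from 29 × 0.166 = 4.8 (Section 4.2.1.3) or 29 × 3/10 = 8.7 (Section 4.2.2.2). The 16.6% covers all Grade 3-5 treatment-related events, two deaths included. The three events in ten patients were a liver abnormality, rhabdomyolysis and hypertension. Both tables order a permanent stop for the Grade 3 liver event, apart from Table 7's declared exception, and hypertension has its own lenvatinib rules in Section 5.3.1.4.1.

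**Conclusion.** The point holds in a limited form: one discretion note of unstated scope, three differences between Tables 7 and 9, and two Table 7 rows at odds with that table's own note. It concerns mainly severe endocrine toxicity. Few of the 29 subjects should be affected, on the assumption that monotherapy rates are a fair guide to this regimen; the true number could be higher if lenvatinib adds to these events. The case for acting rests on subject safety and consistent conduct across sites, not on any effect on the primary analysis. The text alone does not show which rule was intended.

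**What to change.** Reconcile Section 5.3.1.3 (Table 7 and its note), Section 5.5.1 (Table 9 and both its notes) and Section 5.7. Specifically:

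- State which Table 9 cells the discretion note covers.
- Bring the two tables into agreement on Grade 4 hyperthyroidism, Grade 3-4 hypophysitis and the restart threshold after Grade 3-4 endocrine events.
- Reconcile the Table 7 note with its hypophysitis and type 1 diabetes/hyperglycemia rows, and say whether it reaches hypothyroidism.
- Name the table that governs if they differ, and repair the cross-reference in Section 5.3.1.3.

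The sponsor's clinicians decide which rule stands in each case; this review takes no position on that. The cost is amendment wording, with no added procedures, visits or subjects.

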5.5.2 Management of Infusion Reactions

Signs and symptoms usually develop during or shortly after drug infusion and generally resolve completely within 24 hours of completion of infusion.

The table below shows treatment guidelines for subjects who experience an infusion reaction associated with administration of pembrolizumab.

Table 10: Infusion Reaction Treatment Guidelines

NCI CTCAE Grade	Treatment	Premedication at subsequent dosing
Grade 1 Mild reaction; infusion interruption not indicated; intervention not indicated	Increase monitoring of vital signs as medically indicated until the subject is deemed medically stable in the opinion of the investigator.	None
Grade 2 Requires infusion interruption but responds promptly to symptomatic treatment (e.g., antihistamines, NSAIDS, narcotics, IV fluids); prophylactic medications indicated for <=24 hrs	
Stop Infusion and monitor symptoms. Additional appropriate medical therapy may include but is not limited to:
 
 IV fluids Antihistamines NSAIDS Acetaminophen Narcotics 
Increase monitoring of vital signs as medically indicated until the subject is deemed medically stable in the opinion of the investigator. If symptoms resolve within one hour of stopping drug infusion, the infusion may be restarted at 50% of the original infusion rate (e.g., from 100 mL/hr to 50 mL/hr). Otherwise dosing will be held until symptoms resolve and the subject should be premedicated for the next scheduled dose.
 
Subjects who develop Grade 2 toxicity despite adequate premedication should be permanently discontinued from further trial treatment administration.
	
Subject may be premedicated 1.5h (\pm 30 minutes) prior to infusion of pembrolizumab (MK-3475) with:
 
Diphenhydramine 50 mg po (or equivalent dose of antihistamine).
 
Acetaminophen 500-1000 mg po (or equivalent dose of antipyretic).

Grades 3 or 4 Grade 3: Prolonged (i.e., not rapidly responsive to symptomatic medication and/or brief interruption of infusion); recurrence of symptoms following initial improvement; hospitalization indicated for other clinical sequelae (e.g., renal impairment, pulmonary infiltrates) Grade 4: Life-threatening; pressor or ventilatory support indicated	
Stop Infusion. Additional appropriate medical therapy may include but is not limited to:
 
 IV fluids Antihistamines NSAIDS Acetaminophen Narcotics Oxygen Pressors Corticosteroids Epinephrine 
Increase monitoring of vital signs as medically indicated until the subject is deemed medically stable in the opinion of the investigator. Hospitalization may be indicated. Subject is permanently discontinued from further trial treatment administration.
	No subsequent dosing
Appropriate resuscitation equipment should be available in the room and a physician readily available during the period of drug administration.		

5.6 Diet, Activity, and Other Considerations

5.6.1 Diet

Subjects should maintain a normal diet unless modifications are required to manage an AE such as diarrhea, nausea or vomiting.

5.6.2 Contraception

Pembrolizumab and lenvatinib may have adverse effects on a fetus in utero. Furthermore, it is not known if pembrolizumab and lenvatinib have transient adverse effects on the composition of sperm.

For this trial, male subjects will be considered to be of non-reproductive potential if they have azoospermia (whether due to having had a vasectomy or due to an underlying medical condition).

Female subjects will be considered of non-reproductive potential if they are either:

(1) postmenopausal (defined as at least 12 months with no menses without an alternative medical cause; in women <45 years of age a high follicle stimulating hormone (FSH) level in the postmenopausal range may be used to confirm a post-menopausal state in women not using hormonal contraception or hormonal replacement therapy. In the absence of 12 months of amenorrhea, a single FSH measurement is insufficient.);

OR

(2) have had a hysterectomy and/or bilateral oophorectomy, bilateral salpingectomy or bilateral tubal ligation/occlusion, at least 6 weeks prior to screening;

OR

(3) has a congenital or acquired condition that prevents childbearing.

Female and male subjects of reproductive potential must agree to avoid becoming pregnant or impregnating a partner, respectively, while receiving study drug and for 120 days after the last dose of study drug by complying with one of the following:

(1) practice abstinence[†] from heterosexual activity;

OR

(2) use (or have their partner use) acceptable contraception during heterosexual activity.

Acceptable methods of contraception are[‡]:

Single method (one of the following is acceptable):

- intrauterine device (IUD)
- vasectomy of a female subject's male partner
- contraceptive rod implanted into the skin

Combination method (requires use of two of the following):

- diaphragm with spermicide (cannot be used in conjunction with cervical cap/spermicide)
- cervical cap with spermicide (nulliparous women only)
- contraceptive sponge (nulliparous women only)
- male condom or female condom (cannot be used together)
- hormonal contraceptive: oral contraceptive pill (estrogen/progestin pill or progestin-only pill), contraceptive skin patch, vaginal contraceptive ring, or subcutaneous contraceptive injection

†Abstinence (relative to heterosexual activity) can be used as the sole method of contraception if it is consistently employed as the subject's preferred and usual lifestyle and if considered acceptable by local regulatory agencies and ERCs/IRBs. Periodic abstinence (e.g., calendar, ovulation, sympto-thermal, post-ovulation methods, etc.) and withdrawal are not acceptable methods of contraception.

‡If a contraceptive method listed above is restricted by local regulations/guidelines, then it does not qualify as an acceptable method of contraception for subjects participating at sites in this country/region.

Subjects should be informed that taking the study medication may involve unknown risks to the fetus (unborn baby) if pregnancy were to occur during the study. In order to participate in the study subjects of childbearing potential must adhere to the contraception requirement (described above) from the day of study medication initiation (or 14 days prior to the initiation of study medication for oral contraception) throughout the study period up to 120 days after the last dose of trial therapy. If there is any question that a subject of childbearing potential will not reliably comply with the requirements for contraception, that subject should not be entered into the study.

